1. STUDY OBJECTIVES

1.1 Primary objective: Determine whether parents perceive Theraworx Foam and Spray to be superior to usual care for *prevention* of diaper dermatitis among infants 1-14 months old.

- Hypothesis #1a: Parents will report fewer total days of diaper dermatitis in their infants when the infants are using Theraworx than when they are not.
- Hypothesis #1b: Parents will less likely to report any diaper dermatitis in their infants when the infants are using Theraworx than when they are not.

1.2 Secondary objectives:

Objective #2: Determine whether Theraworx Foam is superior to usual care for reduction of severity of diaper dermatitis among infants 1-14 months old.

- Hypothesis #2a: Parents will report less use of adjuvant topical treatments (antifungals, antibacterials, steroids) for their infant's diaper dermatitis when they are using Theraworx than when they are not.
- Hypothesis #2b: Parents will report less severe diaper dermatitis based on visual assessment when their infants are using Theraworx than when they are not.

Objective #3: Determine parents' satisfaction with Theraworx Foam

- Hypothesis #3a: Parents will find Theraworx easy to apply and remove
- Hypothesis #3b: Parents will find Theraworx pleasant to use (smell, feel, appearance)

2. BACKGROUND

Diaper dermatitis is one of the most common dermatologic diseases affecting infants and children (Tuzun et al., 2015). The incidence is highest among those 9-12 months old and it has been reported to affect 7-50% of infants in the US (Tuzun et al, 2015, Cohen, 2017, Blume-Petavi & Kanti, 2018). It is caused by skin exposure to a combination of several factors including: excessive moisture, topical irritants, reduced pH, friction, maceration and bacterial infection (Blume-Petavi & Kanti, 2018). When infants soil their diaper, diaper contents saturate the area raising the pH of the skin above the normal level of 5 or less, and leaving the area highly vulnerable to maceration from friction. Irritants in urine and feces are then able to penetrate the macerated skin, causing inflammation and greater skin friability (Pogacar et al., 2018). An elevation in the skin pH allows pathogenic bacteria to overgrow, and combined with the breakdown in the skin's outer epithelial barrier (statum corenum), can lead to bacterial infection (Pogacar et al., 2018). With the development of more advanced and absorbent diapers in recent years, the incidence of diaper dermatitis has subsequently decreased (Blume-Petavi & Kanti, 2018). Another primary preventive practice for reducing the risk of diaper dermatitis is use of prophylactic barrier creams (Kayaoglu, Kivanc-Altunay & Sarikaya, 2015). Nonetheless, while disposable diaper technology has become more advanced, the composition of barrier creams has not. In fact, some barrier creams such as those containing zinc oxide may actually contribute to the damage cascade leading to diaper dermatitis by increasing the pH of skin (Bartels, et al., 2014).

Theraworx Spray Foam by Avadim Health, Inc. is an FDA-registered OTC drug (NDC 61594-000). The marketed product is labelled as a skin protectant with use "for temporary protection of minor cuts, scrapes, burns and chapped or cracked skin" with the active ingredient being allantoin. Allantoin is listed on the FDA OTC Ingredient List as used for or having reviews pending for use as a wound healing agent, skin protectant and external analgesic. As such, Theraworx Foam used in the diaper area may be beneficial for protecting skin against diaper dermatitis wounds, as well as for assisting with wound healing and reducing any associated pain. The purpose of this study is to determine parents' perceptions of the benefits of using Theraworx Spray Foam on their infant's diaper area as part of their hygienic routine, including whether they feel the product is pleasant and easy to use, and whether they feel it helps prevent and reduce the severity of diaper dermatitis in their infants 1-14 months old. This investigation is not intended to be reported to FDA in support of a new indication for use, to support any other significant change in the labeling or to support a significant change in the advertising.

3. PROTCOL DESIGN AND OVERVIEW:

3.1 Study design: This study will be conducted as an open-label, unblinded, sequential trial in which we will employ a pre- vs. post-intervention design involving a run-in period followed by a trial period for all participants. In this way, infants will serve as their own control limiting variability between comparator groups in terms of

diaper hygiene practices including frequency of diaper changes and type of diapers, wipes, and other products used.

3.3 Study Timeline:

	Study month											
Activity	1	2	3	4	5	6	7	8	თ	10	11	12
Recruit and enrollment	Х	х	Х	Х	Х	Х	Х	Х	Х			
Participant run-in period	Х	х	Х	Х	Х	Х	Х	Х	Х			
Participant experimental period		х	Х	Х	Х	Х	Х	Х	Х	х		
Data analysis											х	х

4. PARTICIPANT ELIGIBILITY

4.1 Description of sites enrolling participants: Caregivers of infants ages 1-12 months old will be recruited from one of the five the Children's Health Centers (CHCs) at Children's National Health System. These health centers together treat ~30% of all children ages 0-18 years old in DC with Medicaid insurance. The population is predominantly minority (African American (85%), Hispanic (8%)) and publically insured (83%).

4.2 Inclusion criteria: Caregivers will be eligible if they can read English at the 8th grade level, and have reliable access to the internet and email for 7 weeks. English proficiency and internet access will be verified by parental completion of the first online survey within 24 hours of the request. Caregivers must also be a custodial guardian of an infant between the ages of 1-12 months old who lives with them, currently wears diapers, and has had \geq 1 diaper rash in the 2 months preceding recruitment.

4.3 Exclusion criteria: Caregivers will be excluded if their infant is immunocompromised, has a congenital disorder, or, on the day of recruitment, has a diaper rash, has a moderate to severe illness requiring hospitalization or transfer to the emergency room, or was circumcised <10 days prior. Participants who do not complete the first online survey or ≥2 post-intervention online surveys will be excluded from participating in the remainder of the study. They will also be excluded if they do not have a stable address at which they can receive a package of Theraworx at week 4 and/or are unable to pick it up at Children's National.

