5. PROCEDURES

5.1 Recruitment and enrollment: Potential participants will be initially identified when bringing their children to one of the five Children's Health Centers for care. On days of recruitment (which will be determined via a convenience sample based on study personnel scheduling), study personnel will access electronic health records to identify potential participants based on the age of their child. Parents of children ages 1-12 months old will be approached for study participation in a private treatment room or in the waiting room. Potential participants will be told briefly that they may qualify to participate in a 7 week study to help determine the effectiveness of a new diaper rash product called Theraworx that is currently being used as a skin protectant and for wound care. They will be told that the study will involve using Theraworx with every diaper change for 4 weeks, and also answering 8 surveys starting with a baseline, in-person survey on the day of enrollment, followed by 7 weekly, online surveys. Those who are interested in learning more about the study will be invited to a private space (if not already in one) to conduct the screening process, and if applicable, the informed consent process (Appendix A). Study eligibility will be assessed using an online screening form with stop logic

(Appendix B). For those who meet eligibility requirements, study staff will obtain written informed consent, verbally administer the baseline, in-person survey, obtain several forms of contact information, demonstrate how the Theraworx Foam should be used, and train participants in rating rash severity using a modified Diaper Dermatitis Scale (Buckley 2016) (Appendix C).

5.2 Run-in and trial periods: There will be a 3 week run-in period starting just after enrollment during which time parents will be instructed to continue their usual diapering care including use of any other diaper products/creams, and to respond to the weekly survey requests. After completing the run-in period, parents will choose to either pick up from the hospital or be sent via Fed-Ex a sufficient supply of Theraworx to last the 4 week duration of the trial period. Parents will receive written instruction on how to apply the Theraworx with every diaper change (Appendix D) and to continue to respond to the weekly survey requests.

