5.3 Surveys

5.3.1 Baseline, in-person survey: Immediately following the informed consent process, study staff will verbally administer the baseline, in-person survey to participants (Appendix E). This survey will assess infant race/gender, diet (breast/bottle feeding/solid food), daily stool frequency, history of parental and sibling atopic dermatitis/childhood eczema, frequency of diaper dermatitis, creams/products used in diaper area (bath soap, emollients, diaper wipes); and who is involved in changing diapers (parent, grandparent, sibling, babysitter, daycare, etc.). It will also determine participant preference to pick up the Theraworx or have it sent to their home, and assess participant accuracy with rating visual severity of diaper rashes according to the modified Diaper Dermatitis Scale after being trained by staff. Lastly, participants will be asked to recall total number of days their infant had a diaper rash over the last 7 days, and if the number is greater than 0, to rate the rash using the modified Diaper Dermatitis Scale.

Upon completion of the baseline, in-person survey, the participant will receive an incentive debit card (ClinCard) which will be activated for the patient and charged with \$10. The participant will be instructed to keep this card for the next 7 weeks to receive future incentive disbursements for completing the online surveys.

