5.3.2 Weekly, online surveys: Starting on the first Monday morning that falls at least 8 days from completion of the baseline, in-person survey and repeating each of the following Monday mornings for a total of 7 occurrences, a unique online survey link will be emailed to each participant. Each Sunday beforehand, participants will be texted and emailed a reminder to check their emails the next day and to complete the survey within 24 hours of receiving the emailed link. Each Monday morning, participants will receive a second text message reminder. By each Tuesday at noon, a list will be generated of survey non-respondents who will be contacted by phone twice that day by study staff to complete that week's survey on the phone. Each Wednesday morning, ClinCards will be charged with incentive awards for participants who complete the entire online survey. Participants who do not complete at least the first online survey will not be eligible to complete any further surveys and will be dropped from the study. This will help limit participation to those who can demonstrate capacity and willingness to complete the online survey with the intent of minimizing loss-to-follow up over the 7-week period of individual enrollment.

Weekly online surveys will assess whether the infant had any diaper dermatitis over the past 7 days, and if so, the total number of days with rash, and severity of rash on its worst day (using a modified Diaper Dermatitis Scale score (0-8)). It will also assess for any: use of other products and adjuvant therapies in the diaper area, diarrheal illnesses, new foods initiated, and changes to their contact information. The surveys during the run-in period (weeks 1-3) will confirm whether the participant prefers to pick up the Theraworx or have it sent to their home (Appendix F). During the trial period (weeks 4-6), the weekly survey will also assess how frequently Theraworx was used, and whether it was applied as a foam and/or spray (Appendix G). The final survey at the end of week 7 will be slightly longer since it will also assess satisfaction with Theraworx (in terms of its smell, feel, appearance, ease of use, whether they would recommend it to a friend, and how it compares to other diaper creams they have used) (Appendix F).

5.4 Participant reimbursement: To promote completion of online surveys and reduce risk of participant loss-to-follow up, an escalating incentive scale will be used. Completion of the baseline, in-person survey and the

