9.3 Statistical Considerations

Hypothesis 1a: Parents will report fewer total days of diaper dermatitis in their infants when the infants are using Theraworx than when they are not. To evaluate Hypothesis 1a, total reported dermatitis days over the 4 week pre- and post-intervention time-points will be separately summed. For the primary analysis, only participants who completed all 8 weekly surveys will be included. Secondary analyses may consider all participants with at least two reports in each of the study periods, with missing values assumed to be the mean number of dermatitis days reported by the participant by study period. Number of dermatitis days during usual care (pre-intervention) will be compared to number of dermatitis days following use of the Theraworx Spray Foam (post-intervention) using either paired t-test or Wilcoxon signed rank test, as appropriate.

Hypothesis 1b: Parents will be less likely to report any diaper dermatitis in their infants when the infants are using Theraworx than when they are not. Occurrence of any dermatitis during the two study periods will be coded as "yes" (at least one dermatitis day) or "no" (zero dermatitis days) based on parent report of number of dermatitis days. Differences in occurrence pre- and post-intervention will be explored using McNemar's test. If numbers permit, conditional logistic regression will be considered to evaluate odds of dermatitis when using Theraworx Spray Foam compared to usual care.

Hypothesis 2a: Parents will report less use of adjuvant topical treatments (antifungals, antibacterials, steroids) for their infant's diaper dermatitis when they are using Theraworx than when they are not. Use of adjuvant topical treatments during each of the study periods will be considered as both a binary variable (any or none) as well as frequency of use, defined as number of weeks in which use was reported. Any use pre- vs. post-intervention will be evaluated using McNermar's test or conditional logistic regression. Number of uses will be compared using Wilcoxon signed rank test. Depending on numbers, marginal homogeneity tests may also be considered, treating the number of weeks as categorical variables. As use during unreported weeks will be unknown and difficult to quantify, primary analyses will consider only participants who completed all surveys.

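### Usual-care data are tied to a rash-free recruitment day, above all in the baseline recall week; the Theraworx period has no such condition and neither period has an onset rule

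*Combined protocol and SAP*

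**What the plan says.** - **Entry.** Section 4.3 excludes infants for whom rash is present at recruitment ("on the day of recruitment, has a diaper rash"). Section 4.2 also requires at least one "diaper rash in the 2 months preceding recruitment".
- **Usual care.** Section 5.2: "There will be a 3 week run-in period starting just after enrollment".
- **Switch.** Section 5.2: "After completing the run-in period, parents will choose to either pick up from the hospital or be sent via Fed-Ex" the supply. The switch depends on finishing the run-in and obtaining the product. Neither Section 5.2 nor the schedule in 5.5 sets or records a rash status at that point.
- **Baseline recall.** Section 5.3.1: "participants will be asked to recall total number of days their infant had a diaper rash over the last 7 days".
- **First online survey.** Section 5.3.2: "Starting on the first Monday morning that falls at least 8 days from completion of the baseline, in-person survey". As described there, each weekly survey asks about any rash in the past 7 days, the number of rash days and worst-day severity, but not when a rash began.
- **Analysis.** Section 9.3 sums all rash days over a four-week period before and after the switch (1a), and codes a period as positive if it holds one rash day or more (1b). Neither has an onset rule. The primary 1a analysis needs eight completed weekly surveys, whereas Section 5.3.2 provides seven.

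**The concern.** The objective is prevention, and each infant is its own control, so the two periods should be measured from comparable states. The entry rule makes one side depend on the outcome: usual-care data lie next to a day on which rash is ruled out. The Theraworx data begin three run-in weeks later with no such condition.

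The baseline week is affected most. The run-in gives three weeks and the online schedule seven surveys. Only the baseline report brings these to four weeks and eight surveys. If it is the fourth pre-intervention report, it contributes seven days that end on a guaranteed clear day.

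In the other direction, a rash that began under usual care and lasts past the switch adds days to the Theraworx total, and one such day makes the infant positive on 1b. At stake is a spurious difference in 1a that is not negligible against a 2-day target, and a 1b result that mixes new rashes with old ones.

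**Working it through.** **1. The plan's own figure.** Inputs from Section 9.2: difference 2 days, SD 5, 80% power, two-sided 0.05, 35% loss. The correlation ρ is called moderate, with no number. SD of the difference = 5√(2(1−ρ)). At ρ = 0.35 this is 5.70; the paired t-test needs 66 pairs, and 65 pairs give 79.6% power. At ρ = 0.40 it needs 61, or 64 with the Wilcoxon factor π/3. So 65 is reproduced for ρ of about 0.35–0.40, and 65/(1 − 0.35) = 100.

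**2. Timing.** The first Monday at least 8 days after baseline falls 10 days later for a Friday recruit and 14 days later for a Monday recruit. With a 7-day recall, the first counted run-in window opens 3–7 days after the rash-free day for weekday recruits.

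**3. Model.** A daily two-state chain with an inert product and no time trend. Let p be the share of days with rash and D the mean episode length. Recovery b = 1/D, onset a = pb/(1−p), λ = 1−a−b. The chance of rash t days before or after a rash-free day is p(1−λ^t). The documents do not give p or D; Section 2's 7–50% is the share of infants affected, not of days. Assumed range: p = 5–20%, D = 3–7 days, gap 3 or 7 days.

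**4. Central case (p = 0.15, D = 5, gap 3).** b = 0.2, a = 0.0353, λ = 0.7647.

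| Window | Days | Expected rash days | Unconditioned (days × p) | Shortfall |
|---|---|---|---|---|
| Baseline recall | 7 | 0.64 | 1.05 | 0.41 |
| Run-in surveys | 21 | 2.93 | 3.15 | 0.22 |
| Pre total | 28 | 3.57 | 4.20 | 0.63 |
| Theraworx | 28 | 4.20 | 4.20 | 0.00 |

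The false excess on Theraworx is 4.20 − 3.57 = 0.63 day, and 0.63/2 is about 30% of the target. Across the assumed range it is 0.1–1.2 days. With p = 7–25%, D = 2–7 and a first survey at 8 or 14 days, it is 0.06–1.9 days.

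**5. Run-in surveys only.** 4.20/4 − 2.93/3 = 0.07 day per week (range 0.001–0.17). Scaled to four weeks the central value is 0.29 day, so dropping the baseline report removes more than half of the 0.63.

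**6. Hypothesis 1b, 28 v 28 days.**
- Pre: no rash = (1−a)^7 × [1 − 0.15(1−λ^4)] × (1−a)^20 = 0.778 × 0.901 × 0.487 = 0.342, so 65.8% positive.
- Theraworx: no rash = 0.85 × (1−a)^27 = 0.85 × 0.379 = 0.322, so 67.8% positive.
- Net difference about 2 points; range 0–3.6.
- Gross carry-over, P(rash at switch) × (1−b) = 0.15 × 0.8 = 12% (range 3–17%), is not this difference.

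**7. Power.** If the true effect is 2 days and ρ = 0.35, 65 pairs give about 68% power with a 0.25-day bias, 55% with 0.5 and 48% with 0.63.

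**8. Does an onset rule for 1b work?** Not with unequal windows. Run-in any rash over 21 days is 1 − 0.901 × 0.487 = 56.1%, all of it begun after the rash-free recruitment day. New-onset rash over 28 Theraworx days is 62.3%. With an inert product that is a 6-point gap, larger than the one being corrected.

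With 21 days in each period and the same rule, let s be the chance of rash on the day before the window. Then no new onset = (1−s)(1−a)^21 + s[(1−b)^21 + b((1−a)^21 − (1−b)^21)/(b−a)] = (1−s)(0.470) + s(0.569).
- Run-in: s = 0.15(1−λ^3) = 0.083, giving 52.2% positive.
- Theraworx: s = 0.15, giving 51.5% positive.

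The gap falls below 1 point.

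**The case against.** **No clean start.** A reader might infer that usual care starts from a rash-free state. On the reading that yields 0.63 day it does not. The baseline recall opens 7 days before the rash-free day, when the model already puts 0.15(1−λ^7) = 12.7% of infants in rash, against 15% at the switch. Old rashes can enter both periods. The effect is a dip in the middle of the pre-period. This stands.

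**The 1b effect is small.** A reader might take the 3–17% carry-over as bias. It is not: many of those infants would have a new rash anyway, and the usual-care windows also take in rashes already under way. The net contrast is 0–3.6 points. This stands.

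**It is mainly a pre-period problem.** In the central case 0.41 of the 0.63 day comes from the baseline report. This stands, and is why the first remedy matters most. The run-in shortfall remains.

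**Opposing biases.** Requiring a rash in the prior 2 months selects infants at a bad time, so later improvement by regression to the mean would favour Theraworx. Open-label parent report can do so too. Neither can be sized from the documents. They do not cancel this component, but they rule out a claim about the overall direction.

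**Carry-over can partly be identified.** Zero rash days in the week-3 survey rules out a rash in progress at that survey. This stands in part: an infant with rash days in week 3 remains ambiguous, and one could begin a rash before the product arrives. The questionnaires (Appendices F and G) are not in the text reviewed, so the statement about survey content rests on Section 5.3.2.

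**Conclusion.** The concern holds in limited form and should be addressed. The entry rule, the absence of a rash record at the switch and the lack of an onset rule are in the text. Reaching the four-week pre-period through the baseline recall makes that week under-read usual care.

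For 1a the false excess on Theraworx is 0.1–1.2 days, central case 0.63 against a target of 2. For 1b it is 0–3.6 points. These sizes rest on assumed rash frequency, episode length and gap, an inert product and no trend. They shrink if rashes are short or the first survey falls late.

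A reader might conclude that the trial as a whole is biased against Theraworx. The documents do not support that. Only this component runs that way, and the net direction is unknown.

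**What to change.** 1. **1a.** State in Section 9.3 that the baseline recall is not part of the pre-intervention total. Compare mean rash days per reported week between the three run-in surveys and the Theraworx surveys, and correct the period length and survey count to match.
2. **1b.** Use three surveys in each period, naming in advance which three Theraworx surveys count. Add the same yes/no item to at least the first counted survey of each period: did any rash begin within this recall window (on Theraworx, after first use)? Code new-onset rash identically in both. Putting the item on every weekly survey would also catch a carried-over rash lasting beyond a week.
3. **Supportive analysis.** Omit the first survey week of each period. In the central case the run-in shortfall falls to 0.15 × (λ^11 − λ^25)/(1−λ)/2 = 0.016 day per week. Restricting to infants with zero rash days in week 3 is an alternative way to remove carry-over. It also sets a third of the run-in record to zero, so it should inform only the Theraworx-period result, not the pre–post difference.

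**Cost.** One survey item and SAP wording, with no added visits or participants and no change to how or when the product is used. The baseline report is lost from 1a and one Theraworx week from 1b. Omitting week 1 drops one of only three run-in surveys, so the supportive analysis is noticeably less precise. Onset not asked about at the time cannot be reliably recovered later.

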7.2 Stopping Criteria

7.2.1 Individual Stopping Criteria

- All protocol interventions are complete
- Failure to complete the first online survey or ≥2 post-intervention online surveys
- Death
- Lost to follow-up
- Study withdrawal
- Serious Adverse Event
- Discretion of the Study PI, such as the PI decides that continuing in the study would be harmful or no longer in the participant's best interest

7.2.2 Study stopping criteria:

- The data show a significantly increased risk of serious adverse effects during the experimental phase of the study.
- It becomes clear that successful completion of the study is not feasible (e.g. there is an excess of patient dropout, missing data, lack of recruitment, etc).

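### The rule that excludes parents for incomplete post-intervention surveys has two readings and, as written, ends the only described adverse-event query and the only satisfaction survey

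*Combined protocol and SAP*

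**What the plan says.** Section 4.3 removes participants who do not complete the first online survey or "≥2 post-intervention online surveys will be excluded from participating in the remainder of the study". Section 7.2.1 lists the same rule as an individual stopping criterion: "Failure to complete the first online survey or ≥2 post-intervention online surveys". It lists "Lost to follow-up" and study withdrawal as separate criteria. Section 5.3.2 spells out only the first-survey part, under which the parent is dropped and gets no more surveys.

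Under Section 5.2, parents receive "a sufficient supply of Theraworx to last the 4 week duration of the trial period" and are told "to continue to respond to the weekly survey requests". Section 5.3.2 provides a list of "survey non-respondents who will be contacted by phone twice that day by study staff", for the purpose of completing that week's survey. It also says: "The final survey at the end of week 7 will be slightly longer since it will also assess satisfaction with Theraworx".

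Section 7.1 makes the weekly online survey the route by which parents report unexpected and serious adverse events, and the schedule in Section 5.5 places adverse-event self-report inside that survey. Section 7.1 also sends all adverse events to the DSMB. One study stopping criterion in Section 7.2.2 reads: "The data show a significantly increased risk of serious adverse effects during the experimental phase of the study".

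**The concern.** There are two linked problems.

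First, the threshold can be read in two ways and no section chooses between them. The requirement in Section 9.3 for at least two reports per period fits Reading B, but it defines an optional secondary analysis set, not a stopping rule. Two coordinators could treat the same family differently.

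Second, the rule ends participation, and the available documents do not say that any data collection continues afterwards. Loss to follow-up and withdrawal have their own entries in Section 7.2.1, so this rule can reach parents who are still contactable and hold product at home. At stake are later adverse-event answers for the DSMB and the study stopping criterion, and the completeness of the satisfaction data.

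**Working it through.** **Inputs.** Section 5.3.2 gives seven online surveys, weeks 1 to 3 in the run-in and weeks 4 to 7 on product, so four count as post-intervention. Section 9.2 gives 65 participants with both measures, 35% loss and 100 recruited. Section 5.4 pays $15 for each of weeks 4 to 6 and $30 for week 7.

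**The plan's own figure.** 65 / (1 − 0.35) = 100, as stated. The rule does not enter this calculation.

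**The two readings.** Four surveys give 16 complete/missed patterns. Two or more missed covers 11 of them and fewer than two completed covers 5, so the 6 patterns with exactly two missed are classified differently. What matters is meeting the rule before week 7:
- Reading A: missing weeks 4+5, 4+6, 5+6, or all three.
- Reading B: missing all three only.

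**Miss rates (assumed).** The documents give no per-survey rate. I assume that 65% complete every survey, either over all 7 online surveys or over the 4 product-period surveys. Let q be the chance of a miss and p = 1 − q.

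*Independent misses.* q = 1 − 0.65^(1/7) = 0.0597 or q = 1 − 0.65^(1/4) = 0.1021.
- Reading A, week-7 response lost: p(3q²p + q³) = pq²(1 + 2p) = 0.0096 or 0.0262.
- Reading A, week-6 response lost (weeks 4 and 5 missed, week 6 would be answered): pq² = 0.0033 or 0.0094.
- Reading B, week-7 response lost: pq³ = 0.0002 or 0.0010.

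*Clustered misses.* Beta-binomial with assumed intraclass correlation 0.2, so a + b = 1/0.2 − 1 = 4, and the mean is solved so that P(no miss) = 0.65.
- 7-survey anchor: mean 0.0950, a = 0.380, b = 3.620. Parents who miss the first survey are dropped before product is supplied, so the calculation must condition on completing week 1. That makes b = 4.620 and a + b = 5.
- 4-survey anchor: mean 0.1341, a = 0.536, b = 3.464, a + b = 4. This anchor already refers to parents on product.

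Write D = s(s+1)(s+2)(s+3) with s = a + b, which is 1680 or 840.
- One specified pattern with two misses: P2 = a(a+1)b(b+1)/D = 0.0081 or 0.0152.
- One specified pattern with three misses: P3 = a(a+1)(a+2)b/D = 0.0034 or 0.0086.
- Reading A, week-7 response lost: 3·P2 + P3 = 0.0278 or 0.0541.
- Reading A, week-6 response lost: a(a+1)b/[s(s+1)(s+2)] = 0.0115 or 0.0238.
- Reading B, week-7 response lost: P3 = 0.0034 or 0.0086.

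| Lost per 100 parents starting product | 7-survey anchor | 4-survey anchor |
|---|---|---|
| Reading A, week 7, independent | 1.0 | 2.6 |
| Reading A, week 7, clustered | 2.8 | 5.4 |
| Reading B, week 7, independent | 0.02 | 0.1 |
| Reading B, week 7, clustered | 0.3 | 0.9 |

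**Secondary analyses.** On Reading A, a parent who misses 4+5, 4+6 or 5+6 is stopped before a second product-period report. On Reading B no such parent exists, because anyone meeting the rule can no longer reach two reports.

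**Incentive cost per 100 starting product, Reading A.** 100 × (30 × week-7 loss + 15 × week-6 loss) = $34 or $93 (independent), $101 or $198 (clustered).

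**The case against.** The strongest reply is that almost nothing is lost. In its ordinary sense, 35% loss to follow-up is permanent dropout, and then the rule removes little further data. On Reading B the loss is near zero. A survey counts as missed only after reminders and two phone calls, so a parent who meets Reading A has gone unreached through two such cycles and may not answer later. All of this stands. It limits the size of the point, and it makes later answers an assumption.

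A reader might infer that the plan abandons safety follow-up in these families. The documents do not support that. The appendices and consent pages are not available and may describe another reporting route. A serious adverse event is itself an individual stopping criterion, yet Section 7.1 still requires it to be documented and reported, so being stopped does not end all safety handling.

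A reader might also infer that the rule biases the main result. It does not bear on the primary analyses of Hypotheses 1a, 2a and 2b, which Section 9.3 restricts to parents who completed every survey; anyone meeting either reading is already outside them. Section 9.3 states no analysis set for 1b, and nothing is claimed about it here. The secondary analyses are optional and Objective 3 is descriptive.

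Finally, it can be said that continuing the surveys overrides a deliberate participation rule. The purpose given in Section 5.3.2, limiting enrolment to parents able and willing to respond, is attached to the first-survey part, which the fix leaves alone.

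**Conclusion.** The point holds as a minor one. The wording has two readings, and on either of them the text as written ends the weekly survey for a parent who meets the rule before week 7 and has not withdrawn. With it go the only adverse-event query described in the available documents and the only source of Objective 3 data. The percentages are illustrative: they rest on reading the 35% as intermittent non-completion and, for the clustered figures, on an assumed correlation of 0.2. The case for changing the text is that these data may be obtainable at very low cost, not that a result is shown to be wrong.

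**What to change.** Add to Sections 4.3 and 7.2.1 that missed post-intervention surveys do not end data collection. The weekly survey with its adverse-event item, and the week-7 satisfaction items, should continue to be offered through the final contact (scheduled Day 50) to everyone who received product and has not withdrawn consent. The first-survey rule stays as it is.

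If the post-intervention part is kept for any other purpose, state whether it counts missed or completed surveys. The documents do not say whether meeting the criterion also affects product use. The sponsor should reconcile Sections 4.3, 5.2 and 7.2.1 on that; no clinical rule is proposed here.

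The change is to protocol wording, since the emails, texts, calls and incentives already exist. It costs a few extra reminder calls and $15 to $30 per extra completed survey, within the total worked out above.
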